#### Response rates

Our goal is to achieve >90% response rates for PROM assessments, recruitment questionnaires, and remote pain assessments. Iterative design cycles will continue with different modes, delivery approaches, follow up for non-response, and preface text.

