#### PROM collection:

The following outcome measures will be collected at baseline (after consent but required before moving on to engagement) and when patients exit the pilot study after 4-5 weeks:

Measure	Domain
Primary	
BPI SF	Pain
Secondary	
	Physical
PROMIS SF	Function
EQ-5D-3L	QoL
PHQ-2	Depression
GAD-2	Anxiety
PROMIS SF	Sleep
Mediators	
PROMIS SF	Self-efficacy

These PROM data will be collected to evaluate the completeness and fidelity of outcome collection rather than to estimate intervention effectiveness. Maximizing PROM response rates and minimizing the proportion of incomplete surveys will be a key focus during our pilot activities. We will offer multiple administration modes for study completion including EHR portal, IVR, telephone interview, and printed questionnaires. The cost and logistics vary considerably across these modes. Their use and acceptance by highly rural and Hispanic individuals has not been characterized. We will therefore query patients regarding their preferred mode during the Recruitment call. After initiating a patients preferred mode we will assess the proportion of responders. We will follow up with non-responders to encourage them to trial an alternative mode. We will capture responses rates to initial and secondary administration modes across demographically-defined subgroups. For persistent non-response, we will attempt to collect PROM data via telephone interview with a CRC.

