#### **Subject Information**

Target accrual is the proposed total number of subjects to be included in this study at Mayo Clinic. A "Subject" may include medical records, images, or specimens generated at Mayo Clinic and/or received from external sources.

Target accrual: 140 (maximum). Accrual will depend on the nature and extent of sociocultural and linguistic tailoring, and the number of iterative design cycles. This total includes 40 participants for the pilot study itself, up to 40 participant interviews, up to 15 study team interviews and up to 45 providers for focus groups.

Subject population (children, adults, groups): Adults

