#### Endpoints:

#### Optimized components and process

Our target endpoint is optimization of key study processes and intervention components. We will use modified, multi-stakeholder Delphi processes to determine when a study process/component has been optimized. A process/component will be considered optimized when 80% of Delphi process participants agree that sociocultural appropriatness, usability, patient-centricity, and acceptability have been optimized. After that point no further iterative refinement cycles will occur.

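### Must the >90% response goal be tied to the final design version, with pilot participants set aside to measure it?

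*Combined protocol and SAP*

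**What the plan says.** The goal is in the Response rates part of the Endpoints section: "Our goal is to achieve >90% response rates for PROM assessments, recruitment questionnaires, and remote pain assessments". The next sentence reads "Iterative design cycles will continue with different modes, delivery approaches, follow up for non-response, and preface text". Neither sentence gives a denominator, a time point or a design version, and neither attaches a consequence to meeting or missing 90%.

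Subject Information sets the numbers: "This total includes 40 participants for the pilot study itself", and "Accrual will depend on the nature and extent of sociocultural and linguistic tailoring, and the number of iterative design cycles". No number of cycles is given there or elsewhere.

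Optimized components and process names the target endpoint, which is refinement of study processes and intervention components. Each is judged separately by a Delphi process with an 80% agreement threshold, and then "After that point no further iterative refinement cycles will occur". Response rate is not one of the qualities on which the panel must agree.

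The PROM collection section says why the instruments are used: "to evaluate the completeness and fidelity of outcome collection rather than to estimate intervention effectiveness". It adds: "Maximizing PROM response rates and minimizing the proportion of incomplete surveys will be a key focus during our pilot activities". The time points are baseline and "when patients exit the pilot study after 4-5 weeks". Response is to be broken down by first and second administration mode and by demographic subgroup. The Measurement section adds completion of pain surveys by mode and of the recruitment questionnaires.

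**The concern.** The things that may vary between cycles (mode, delivery, chasing of non-responders, introductory text) are the things that determine response. The process being scored can therefore change while it is scored. A rate over all 40 mixes abandoned procedures with the ones finally kept. A rate over the last cycle describes the right procedures but may rest on a handful of people. The plan does not choose between the two and sets nobody aside for the final procedures.

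What would be at stake is the pilot's message about completeness of outcome collection. A reader could take comfort from a small last cycle that happened to respond in full, or be discouraged by a pooled rate pulled down by early procedures. The breakdowns by mode and subgroup do not separate the versions. The small-number worry applies to PROMs and pain surveys from enrolled participants. It does not apply to recruitment questionnaires, which go to a much larger, unstated number of screened patients.

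**Working it through.** **Inputs from the document.** 40 pilot participants (Subject Information); goal above 90% (Response rates); 20 Hispanic and 20 rural participants anticipated (Future trial endpoints). The accrual total reproduces: 40 + 40 + 15 + 45 = 140. The plan gives no precision or power figure for the 90% goal, so there is none to reproduce.

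**Assumptions.** Cycles of equal size, numbering 1, 2, 4 or 8; true response of 80% or 95%; every procedure changing at once between cycles. None of these is in the document.

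**Formula.** With n people on the last version, let k be the smallest count with k/n > 0.90. The chance of showing above 90% at true rate p is P(X ≥ k), with X binomial(n, p). Intervals are exact (Clopper-Pearson) 95%.

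| Cycles | n on last version | k needed | Shows >90% if true rate is 80% | Misses if true rate is 95% | 95% interval at k/n |
|---|---|---|---|---|---|
| 1 | 40 | 37 | 2.8% | 13.8% | 79.6% to 98.4% |
| 2 | 20 | 19 | 6.9% | 26.4% | 75.1% to 99.9% |
| 4 | 10 | 10 | 10.7% | 40.1% | 69.2% to 100% |
| 8 | 5 | 5 | 32.8% | 22.6% | 47.8% to 100% |

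For example, with n = 10 and p = 0.80, P(X = 10) = 0.80^10 = 0.107; with n = 20, 20 × 0.80^19 × 0.20 + 0.80^20 = 0.0576 + 0.0115 = 0.069.

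**Pooling can reverse the reading.** With invented counts of 15/20 on a superseded version and 19/20 on the last, the pooled rate is (15 + 19)/40 = 34/40 = 85%, below the goal. The last version alone is at 95%, above it.

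**Would reserving participants help?** Take the last 20 of the 40. The second row of the table applies: 6.9% and 26.4%, against 2.8% and 13.8% with all 40 on one version. If all n respond, the exact lower limit is 0.025^(1/n). It exceeds 0.90 only when n > ln(0.025)/ln(0.90) = 35.01, that is, from 36 people, nearly the whole pilot. A block of 20 leaves 40 − 20 = 20 for refinement. If split evenly over the two subgroups, the block holds 10 of each.

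**Is there a single final version?** The Delphi rule closes each process or component on its own, so they can be fixed at different times. Mode also varies within a person: the PROM collection section starts with the preferred mode, moves non-responders to another, and ends with a coordinator's telephone call. Some of the mode changes named under Response rates may be this sequence. Equal whole-package cycles are therefore a simplification.

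**The case for a change.** The best case for a change is that even a descriptive rate needs a numerator, a denominator and an object. The Data Analysis section itself says that endpoint analysis plans are appropriate for exploratory work. The pilot exists to inform the full trial, PROM completeness is a declared focus, and a few sentences would settle the point. Reading the text as cycling until 90% is reached makes matters worse: with four cycles of 10 and a constant true rate of 80%, at least one cycle shows above 90% with probability 1 − (1 − 0.107)^4 = 36.5%.

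The textual facts in this case stand. No version is named, the number of cycles is open, and the breakdowns are by mode and subgroup only. It is also true that exit response is the informative figure, since baseline PROMs must be completed before a participant moves on.

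The need for a change does not stand. The probabilities of passing and missing describe a decision that the plan never takes. The document does not say that cycles run until 90% is reached; the only stated rule that ends them is Delphi agreement. Nor would the last-cycle rate simply carry over to the trial. The Hypothesis section speaks of integrating intervention components and does not mention the PROM-collection process. The planned secondary measures for the trial include computerized adaptive tests, whereas the pilot's PROM table lists short forms.

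**Conclusion.** The gap is real but small, and no change to the plan follows. The missing detail is a scoring convention for a descriptive goal. A team that refines its procedures in cycles has to look at response cycle by cycle in order to refine them. It can show those counts beside the pooled rate, with baseline and exit kept apart, without a written rule. The reader can then see how few people stand behind any last-cycle figure.

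The one substantive alternative, holding back about 20 of 40 for the final procedures, is a trade-off that the sponsor may fairly decline. It takes half the sample from optimization, the stated endpoint, and presumes one final version. The interval is still 75.1% to 99.9% at 19/20. If refinement does not fit in the first 20, it could need up to 20 more participants.

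The sizes in the table rest on assumed cycle counts, equal splits and true rates. The 32.8% figure in particular needs eight cycles of five. The conclusion would differ if the 90% goal were made a go/no-go criterion for the full trial; nothing in the document does that.

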#### *Oualitative data*

We will incrementally and iteratively develop a coding scheme beginning with the first transcript. Categories, groups of content sharing common features, will be created and abstraction of the text will be accomplished by assigning category codes. Subcategories will be identified to further delineate the content. Finally, themes or ideas that cut across categories will be created. As new concepts emerge, they will be defined and added to the coding scheme. If data saturation is not reached we will consider the need for additional interviews.

Future trial endpoints

Primary: Brief Pain Inventory

Secondary: PROMIS Physical Function, Sleep Disturbance and Anxiety Computerized Adaptive Tests We will assess the psychometric performance of the PROM study endpoints in target subgroups. In addition to calculating descriptive statistics for primary and secondary outcomes at baseline and when participants go off study, we will graph PROM scores in aggregate and by demographically-defined subgroups to assess for ceiling and floor effects and distribution of scores across the full trait range. Although the anticipated sample sizes will be limited, 20 Hispanics and 20 rural dwellers, we will compare measures of central tendency and variance in participants' PROM scores to those reported for other cohorts and used to calculate the full trial's sample size. This will clarify the whether review of the trial's power calculation is warranted.

Effective: 9/20/2017
